2. INTRODUCTION

This statistical analysis plan (SAP) for Protocol No. NCIG-007R, "Randomized, Double Blind, Placebo-Controlled Trial of the Efficacy of Intranasal Oxytocin for the Treatment of Alcohol Use Disorder" describes and expands upon the analytical plan presented in the protocol.

This document contains all planned analyses, reasons and justifications for these analyses for all study data. This plan also includes sample tables, figures, and listings that will be populated. The SAP will follow the International Conference on Harmonization of Technical Requirements for Registration of Pharmaceuticals for Human Use (ICH) Guidelines as indicated in Topic E3 (Structure and Content of Clinical Study Reports), Topic E8 (General Considerations for Clinical Trials) and Topic E9 (Statistical Principles for Clinical Trials). The structure and content of the SAP provides sufficient detail to meet the requirements identified by the Food and Drug Administration (FDA) and ICH.

The following sources were used in preparation of this SAP:

- Protocol # NCIG-007R, Protocol Version No.: 4.0; Version Date: 05Jul2022
- ICH Guidance Topics E9, E3 and E8

3. PROTOCOL SUMMARY

3.1 Study Objectives

3.1.1 Primary

The primary objective of the study is to compare the efficacy of intranasal oxytocin in reducing the weekly percentage of heavy drinking days over the 10 weeks of maintenance treatment among subjects with moderate to severe Alcohol Use Disorder (AUD). A "heavy drinking day" is 4 or more drinks per drinking day for women and 5 or more drinks per drinking day for men.

3.1.2 Secondary

Secondary objectives include assessment of other measures of the effects of oxytocin compared with placebo on reduction of alcohol use as well as effects on alcohol craving, alcohol-related consequences, cigarette smoking and other nicotine use, psychological assessments, retention in the study, and safety and tolerability throughout the study.

3.2 Study Design

This study is a double-blind, randomized, placebo-controlled, parallel group, multi-site clinical trial designed to assess the efficacy of oxytocin compared with placebo to reduce drinking in 100 subjects (50 in each group) who report 4 or more Diagnostic and Statistical Manual of Mental Disorders – Fifth Edition (DSM-5TM) symptoms of AUD. This study will be conducted at 4 clinical sites. If eligible for the study, subjects will be randomized using a stratified permuted block randomization procedure with "clinical site" as a stratification variable in an approximate 1:1 ratio (targeting 50 subjects per group) to receive either intranasal oxytocin or placebo for 12 weeks.

[figure not shown]
If eligible for the study, subjects will receive blinded intranasal oxytocin at 35 IU once per day or intranasal placebo (same volume once per day) for 2 weeks (initial tolerability assessment period), then for the next 10 weeks (maintenance period) subjects will receive oxytocin at 35 IU/twice per day (BID, totally daily dose 70 IU) or intranasal placebo (same volume twice per day)

Subjects will be seen in the clinic at screening visit(s), at randomization, and at Weeks 2, 3, 4, 6, 8, 10, and 13. During the alternate weeks when subjects will not be coming into the clinic (Weeks 5, 7, 9, 11, and 12), subjects will be contacted once during that week by telephone to encourage study drug compliance and to assess withdrawal, adverse events (AEs), and concomitant medication use. A final follow-up telephone interview will occur during Weeks 14/15 (1-to-2 weeks after the end of dosing).

Enrollment will be halted if 2 or more at least possibly related SAEs as judged by the investigator or medical monitor occur. If this occurs, a DSMB meeting will be convened and a decision, in conjunction with the study Sponsor, will be made regarding stopping the study.

The overall study schema is provided in Figure 1. The study schedule of visits and assessments is shown in Table 1.

Figure 1. Overview of Study Design

*Telephone contact, otherwise visit is in clinic

Oxytocin for Alcohol Use Disorder Protocol Number: NCIG-007R

Table 1. Schedule of Assessments

	Screen						ľ	Mainte	nance					EOS ^a	Safety Follow-up
Study Week	-2 to -1	1	2	3	4	5	6	7	8	9	10	11	12	13	14/15
Clinic Visit #	1	2	3	4	5		6		7		8			9	
Informed Consent	X														
Alcohol Breathalyzer	X	X	X	X	X		X		X		X			X	
Urine Drug Screen ^b	X	X	X	X	X		X		X		X			X	
Locator Form	X														
Demographics	X														
Medical/Surgical History	X	X ^c													
Physical Exam	\mathbf{X}^{d}	X	X	X	X		X		X		X			X	
MINI V 7.0.2 (AUD module at EOS)	X													X	
C-SSRS		X	X				X		X		X			X	
Clinical Chemistry ^e	X						X		X		X			X	
Vital Signs	X	X	X	X	X		X		X		X			X	
ECG (12-lead)	X													X	
Prior and Concomitant Meds	X	X	X	X	X	X	X	X	X	X	X	X	X	X	X
CIWA-AR	X	X	X	X	X		X		X		X			X	
Eligibility Checklist	X	X ^c													
Drug Compliance – Diary review		X	X	X	X		X		X		X			X	
Drug Accountability (vial weight)		X	X	X	X		X		X		X			X	
Pregnancy Test/Female Birth Control Methods	X	X	\mathbf{X}^{f}				X		X		X			X	
Weight	X						X		X		X			X	
Drinking Goal	X														
AEs/SAEs			X	X	X	X	X	X	X	X	X	X	X	X	X
Other Services Used for Alcohol Use		X												X	
Problems ^g		Λ												A	
RANDOMIZATION		X													
Brief Telephone Interview ^h						X		X		X		X	X		
Take Control		X	X	X	X		X		X		X				
Exit Interview														X	
Treatment Referral														X	
Follow-Up Telephone Interview															X
Final Subject Disposition															X
Subject Reported Outcomes															

Statistical Analysis Plan: Protocol NCIG-007R, Version 1.0 Dated: 7 Sep 2023

Oxytocin for Alcohol Use Disorder Protocol Number: NCIG-007R

	Screen				Maintenance							EOS ^a	Safety Follow-up		
Study Week	-2 to -1	1	2	3	4	5	6	7	8	9	10	11	12	13	14/15
Clinic Visit #	1	2	3	4	5		6		7		8			9	
Hyperkatifeia Scale		X												X	
Barrett Impulsivity Scale		X													
Spielberger Trait Anxiety Inventory		X													
BPAQ - SF ⁱ		X					X		X		X			X	
Simplified Nutritional Appetite Questionnaire		X					X		X		X			X	
Cigarette and other nicotine use		X					X		X		X			X	
ECR-RS ^j		X					X		X		X			X	
IDS-30 ^k		X													
POMS		X					X		X		X			X	
PROMIS – alcohol negative consequences		X					X		X		X			X	
PROMIS – sleep disturbances		X					X		X		X			X	
PROMIS – pain interference		X					X		X		X			X	
UPSIT ¹		X		X			X		X		X			X	
Urge to drink questionnaire		X					X		X		X			X	
Timeline followback (TLFB)	X	X	X	X	X		X		X		X			X	
Brief Drinking Questionnaire ^m														X	

^a EOS=end of study. These assessments are to be done at Week 13 or if the subject discontinues early and agrees to a final clinic visit.

^b Test for opioids, cocaine, amphetamines, methamphetamine, THC, buprenorphine, methadone, benzodiazepines, oxycodone, 3,4-methylenedioxy-methamphetamine (MDMA), and barbiturates.

^c Updated prior to randomization.

^d Complete physical exam at screening including examination of the nares, plus examination of the nares at all other visits as indicated.

^e AST, ALT, total bilirubin, creatinine, sodium, and potassium.

f Only birth control methods are collected at this visit.

^g At baseline asks about lifetime treatment use and at EOS asks "since beginning this study"

^h AEs, concomitant medications, and drug compliance reminder.

ⁱ Buss Perry Aggression Questionnaire – Short Form

Experiences in Close Relationships—Relationship Structures Questionnaire (ECR-RS) (attachment related anxiety)

^k Inventory of Drinking Situations

¹ University of Pennsylvania Smell Identification Test

^mOnly asked to subjects who request to withdraw from the study and are not willing to provide TLFB drinking data. This questionnaire will be asked at whatever constitutes the EOS visit.

3.3 Study Endpoints

3.3.1 Primary Efficacy Endpoint

The primary efficacy endpoint is the weekly percentage of heavy drinking days during the 10 week maintenance period (study weeks 3-12). A "heavy drinking day" is 4 or more drinks per drinking day for women and 5 or more drinks per drinking day for men.

3.3.2 Secondary Efficacy Endpoints

Secondary endpoints that will be analyzed during the 10-week maintenance period (study weeks 3-12)include:

- 1. Percentage of subjects with no heavy drinking days during treatment
- 2. Percentage of subjects abstinent from alcohol during treatment
- 3. Percentage of subjects with a WHO drinking risk category decrease during treatment of:
 - a. At least 1-level
 - b. At least 2-levels
- 4. Endpoints analyzed monthly and with 1- and 2-month grace periods:
 - a. Percentage of subjects with no heavy drinking days during the period
 - b. Percentage of subjects abstinent from alcohol during the period
 - c. Percentage of subjects with WHO drinking risk category decrease during the period of:
 - at least 1 level
 - at least 2 levels
- 5. Percentage of days abstinent per week
- 6. Weekly mean number of drinks per week
- 7. Weekly mean drinks per drinking day
- 8. MINI AUD symptoms at end of study
- 9. Cigarettes smoked per week among smokers
- 10. Abstinence from cigarette smoking
- 11. Days used other nicotine products per week
- 12. Abstinence from nicotine use
- 13. Experiences in Close Relationships—Relationship Structures Questionnaire (ECR-RS) (attachment related anxiety)
- 14. PROMIS alcohol-related negative consequences
- 15. PROMIS sleep disturbances
- 16. PROMIS pain interference

- 17. Profile of Moods States (POMS) (including subscales)
- 18. Urge to Drink Scale (UDS)

3.3.3 Exploratory Efficacy Endpoint

Hyperkatifeia Scale score at end of study

3.3.4 Safety Endpoints

Safety endpoints will be analyzed over the entire treatment and follow-up period.

- 1. Vital signs
- 2. Physical examination of the nasal mucosa
- 3. Smell testing with the University of Pennsylvania Smell Identification Test (UPSIT)
- 4. Blood chemistries
- 5. Urine drug screen results
- 6. Blood alcohol concentration (BAC) by breathalyzer
- 7. AEs/SAEs
- 8. Electrocardiogram (ECG) results
- 9. Clinical Institute of Withdrawal Alcohol Revised (CIWA-AR) scores
- 10. Frequency of subjects with suicidal ideation at any time during the treatment period Columbia-Suicide Severity Rating Scale (C-SSRS)
- 11. Change in appetite Simplified Nutritional Appetite Questionnaire (SNAQ) scores and percentage of subjects with SNAQ scores ≤14.
- 12. Buss-Perry Aggression scores (BPAQ)

3.3.5 Compliance

Compliance will be assessed using the Subject Diary and by weighing the used study drug vials prior to and after use to calculate the amount dispensed.

4.0 DEFINITION OF ANALYSIS SETS

The study analysis populations will consist of the following:

Full Analysis (FA) Set: The full set is defined as subjects randomized to participate in the study who took at least one dose of investigational product. The full analysis set will be used to evaluate all efficacy and safety endpoints.

5.0 ASSESSMENT AND JUSTIFICATION OF STUDY ENDPOINTS

5.1 Alcohol Consumption Endpoints

5.1.1 Daily Quantity of Alcohol Consumption

Drinking will be assessed using the TLFB methodology (Sobell et al., 1992). The TLFB is a semi-structured interview that provides estimates of the daily quantity of alcohol consumption during specified time periods. It uses a calendar prompt and a number of other memory aids (e.g., holidays, payday, and other personally relevant dates) to facilitate accurate recall of drinking or other drug use during the target period. The procedure has been widely used in clinical and research contexts. It has demonstrated adequate levels of reliability and validity when administered as an in-person interview, over the telephone, and when administered via computer (Carey 1997; Sobell et al., 1988; Sobell et al., 1996).

After consent is signed, the TLFB interview will be performed for the 28-day period prior to signing consent. Thereafter, the interview will be for the previous days between the last assessment and the day prior to the day of the assessment.

If a subject requests to withdraw from the study but agrees to continued telephone contact to assess drinking, the TLFB will be performed over the phone for the duration of the study at a frequency acceptable to the study subject and site staff.

5.1.2 Drinking Days

A drinking day is one calendar day in which the subject reported any alcohol consumption (i.e., > 0 standard drinking units [SDUs]). A standard drink contains approximately 0.6 fluid ounces (oz) of pure alcohol. The data given by the subjects on amount and type of alcoholic beverage(s) consumed will be converted to SDUs. An Excel spreadsheet customized for use in this study will be used for double data entry by clinical site staff to collect the TLFB drinking data. This spreadsheet contains a calculator to determine standard drink units (SDUs). Standard drink unit definitions are provided in Table 2.

Table 2: Standard Drink Unit Definitions

For Beer (~ 5% alcohol), the approximate number of SDUs in:

- 12 oz = 1.0
- 16 oz = 1.3
- 24 oz = 2.0
- 40 oz = 3.3

For malt liquor ($\sim 7\%$ alcohol), the approximate number of SDUs in:

- 12 oz = 1.4
- 16 oz = 1.9
- 22 oz = 2.6
- 40 oz = 4.7

For table wine (~ 12% alcohol), the approximate number of SDUs in:

- 750 mL bottle = 25 oz = 5.0
- 5 oz glass = 1.0

• 10 oz glass = 2.0

For 80 proof spirits ($\sim 40\%$ alcohol), or hard liquor, the approximate number of SDUs in:

- 1.5 oz (mixed drink) = 1.0
- 12.7 oz (pint) = 8.5
- 25 oz (a fifth)= 17.0
- 1.75 L (59 oz) = 39.0

5.1.3 Heavy Drinking Day

A heavy drinking day is defined as a day with 5 or more drinks (SDUs) for males and 4 or more drinks (SDUs) for females.

5.1.4 Days at Risk

If a subject is being treated at an inpatient facility, is incarcerated, or otherwise under confinement, each day spent in under these conditions is considered a reduction in the days at risk for drinking and is deducted from the denominator in calculations of rates of drinking days.

5.1.5 Weekly Percentage of Heavy Drinking Days and Weekly Percentage of Days Abstinent

Weekly percentage of heavy drinking days is the number of heavy drinking days in a 7-day period divided by 7 then multiplied by 100. The TLFB permits capturing data in a subsequent visit if a visit is missed; however, if fewer than 7 days are observed, then the denominator is the number of days observed in the 7-day period. At least 3 days in a week must be observed; otherwise, the week is considered missing.

Weekly percentage of days abstinent is similarly calculated by using the number of days abstinent instead of the number of heavy drinking days.

5.1.6 Percentage of Subjects with No Heavy Drinking Days and the Percentage of Subjects Abstinent from Alcohol

The percentage of subjects with no heavy drinking days is the number of subjects that have no heavy drinking days during the period of interest divided by the number of subjects with at least one day of non-missing drinking data during the period of interest, multiplied by 100.

The percentage of subjects abstinent from alcohol is calculated similarly, except the numerator is the number of subjects that have no drinking days during the period of interest.

5.1.7 Weekly Mean Number of Drinks and Weekly Mean Number of Drinks per Drinking Day

Weekly mean number of drinks is the sum of SDUs calculated to the tenths over 7 calendar days divided by the number of days with non-missing data. The quotient is multiplied by 7. At least 3 days in a week must be observed; otherwise, the week is considered missing.

Weekly mean number of drinks per drinking days utilizes the same numerator, and the denominator is the number of days with greater than 0 SDUs. Weeks where all days within the week are abstinent are assigned a value of 0 for weekly drinks per drinking day.

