Analysis of the Secondary Efficacy Endpoints: Analysis of the continuous secondary endpoints (weekly mean drinks per week, weekly mean drinks per drinking day, percentage of days abstinent, number of cigarettes smoked per week, number of days of other nicotine product use per week, POMS scores, ED-RS scores, PROMIS scores, Urge to Drink Scores will be analyzed in a similar fashion to that of the primary outcome (except substituting baseline equivalent of the outcome as a covariate). Analysis of the dichotomous secondary outcomes (percentage of subjects with no heavy drinking days, percentage subjects abstinent from alcohol, percentage of subjects with 1- and 2-level decreases in WHO drinking categories, and percentage of smokers abstinent from smoking) will be conducted via logistic regression of the endpoint measured across the entire treatment period (monthly and with grace periods, as specified). Secondary analyses to satisfy statistical hypotheses will be performed on data collected during the 10-week maintenance period; however, as appropriate, descriptive statistics will be used to present these data during the initial 2-week period as well. Covariate selection beyond treatment group, clinical site, and baseline equivalent of the endpoint will be specified in the SAP. No imputation will be used for the analysis of secondary endpoints.

**Exploratory Analysis**: A number of variables will be tested as potential moderators of the medication treatment effect on the percentage of heavy drinking days primary endpoint. Weeks 3-12 will be the period of interest. Continuous moderator variables will be dichotomized. The potential moderator variables that will be examined include measures of anxiety and depression (ECR-RS subscales of attachment and anxiety, POMS subscales of depression and anxiety, Spielberger Trait Anxiety Inventory, and Barratt Impulsiveness Scale), and those suggestive of alcohol withdrawal (i.e., withdrawal question on the MINI for alcohol use disorder), and alcohol-related treatment goal.

There is interest in exploring the use of a new Hyperkatifeia Scale as a predictor and moderator of drug response Exploratory analyses utilizing Hyperkatifeia Scale scores will include: 1) conducting moderator analyses using total

score; 2) comparison of change from baseline between treatment groups for total score and subscales.

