# 10.12. Brief Drinking Questionnaire

If a subject is withdrawn from the study early and is no longer participating in clinic visits or providing TLFB drinking data but is willing to be contacted by phone at the week most proximal to dropout, then they will be administered the Brief Drinking Questionnaire. The questions are taken from the list recommended by the NIAAA Task Force on Recommended Alcohol Questions (Oct 15-16, 2003) and ascertain: if there was any drinking during the target period; if so, how many a day on average; the largest number of drinks consumed on any one day; and, the number of times reaching the heavy drinking limit (4 or more for women and 5 or more for men). This data will be recorded on a source document and eCRF. This does not apply to subjects who are willing to supply daily drinking data by the TLFB method.

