#### 11.4.3. Secondary Efficacy Endpoints Analysis

Analysis of the continuous secondary endpoints (weekly mean drinks per week, weekly mean drinks per drinking day, percentage of days abstinent, number of cigarettes smoked per week, number of days of other nicotine product use per week, POMS scores, ECR-RS scores, PROMIS scores, and Urge to Drink scores will be analyzed in a similar fashion to that of the primary outcome (except substituting baseline equivalent of the outcome). Analysis of the dichotomous secondary outcomes (percentage of subjects with no heavy drinking days, percentage subjects abstinent from alcohol, percentage of subjects with 1- and 2-level decreases in WHO drinking categories, and percentage of smokers abstinent from smoking) will be conducted via logistic

regression of the endpoint measured across the entire treatment period (monthly and with grace periods, as specified). Secondary analyses to satisfy statistical hypotheses will be performed on data collected during the 10-week maintenance period; however, as appropriate descriptive statistics will be used to present these data during the initial 2-week period as well. Covariate selection beyond treatment group, clinical site, and baseline equivalent of the endpoint will be specified in the SAP. These analyses will be performed using the Full Analysis Set subjects with no imputation for missing data.

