9.5 Handling of Missing Data

9.5.1 Missing Data for Continuous Endpoints

Drinking data is collected in the TLFB. Prior to the subject dropping out of the study, every attempt will be made to continue to collect TLFB data. However, if the subject no longer wishes to participate in the collection of the TLFB, but agrees to a shorter drinking assessment using the Brief Drinking Questionnaire (BDQ), then, answers from the BDQ will be used in conjunction with the TLFB (if some TLFB data were provided by the subject) or in lieu of the TLFB (if no data were provided by the subject) to otherwise avoid missing data for drinking endpoints. Specifically, the BDQ has two questions assessing whether the subject had any heavy drinking days or drinking days during the period covered and will be used to assess the presence of a heavy drinking day or or a drinking day, respectively, for the drinking endpoints percentage of subjects with no heavy drinking days and percentage of subjects abstinent, respectively.

The primary analysis of the primary endpoint will be performed on available data in the Full Analysis Set with no imputation for missing data. However, a sensitivity analysis will be performed on the primary endpoint using multiple imputation for missing drinking data (Jakobsen et al, 2017). Multiple imputation replaces each missing value with a set of "m" plausible values that represent the uncertainty about the right value to impute. The multiple imputation method will be performed on transformed endpoint data, if a transformation is deemed necessary. The data will be evaluated for the pattern of missingness. If the data have monotone missingness then the regression method will be used. If the data have non-monotone missingness then the Monte Carlo method will be used (Ratitch et al, 2013). The imputation model will include a limited set of variables likely to be associated with missingness on the primary endpoint, excluding treatment assignment. The variables may include but are not limited to site, time and baseline alcohol use. The "m" imputed datasets each will be analyzed using mixed effects models then SAS PROC MIANALYZE will be used to combine the parameter estimates.

No imputation will be done for analysis of secondary endpoints.

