9.7 Drug Exposure and Retention

Medication compliance, defined as the amount of investigational product taken as a proportion of the total amount prescribed per protocol, will be evaluated for the oxytocin and placebo groups based on the Subject Diary. Average IU per day of investigational product taken based on the the vial weight difference prior to and after dispensment will also be reported overall and weekly will be reported for the oxytocin and placebo groups. Exposure and compliance averages will be compared across treatment groups using t-tests at each week and overall. If the data are meaningfully skewed then the Wilcoxon rank-sum test will be used. The same test will be used for each week and overall. The research participation rate, defined as percentage of subjects with complete drinking data, will be compared between treatment groups. A Fisher's Exact test will

be used for the overall participation rate, weekly tests will not be performed. In addition, the percentage of subjects discontinuing medication or early withdrawal from the study and a listing of these reasons for discontinuation will be provided. No statistical inference will be performed for reasons of discontinuation.

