f you were to need treatment in the future, would you choose to				0.xxx
Definitely yes	xx (xx.x%)	xx (xx.x%)	xx (xx.x%)	
Generally yes	xx (xx.x%)	xx(xx.x%)	xx (xx.x%)	
Neither yes or no	xx (xx.x%)	xx (xx.x%)	xx (xx.x%)	
No, not really	xx (xx.x%)	xx(xx.x%)	xx (xx.x%)	
Definitely not	xx (xx.x%)	xx(xx.x%)	xx (xx.x%)	
Refuse to answer	xx (xx.x%)	xx(xx.x%)	xx (xx.x%)	
Missing	XX	Xx	XX	
How much do you think of yourself as wanting to please other po	 	er)?		0.xxx
More than average	xx (xx.x%)	xx (xx.x%)	xx (xx.x%)	0.7272
Average	xx (xx.x%)	xx (xx.x%)	xx (xx.x%)	
Less than average	xx (xx.x%)	xx (xx.x%)	xx (xx.x%)	
Refuse to answer	xx (xx.x%)	xx (xx.x%)	xx (xx.x%)	
Missing	XX	Xx	XX	
0		.1 ****1	1 1 1 1 1 1 1 1 1 1 1 1 1 1 1 1 1 1 1 1	

¹p-value from t-test for continuous variables (t) – skewed continuous data uses the Wilcoxon rank-sum test (w) - chi-square test for categorical variables (c).

Table 9: Research Participation by Treatment Group and Week

		Placebo (N=x	x)		Oxytocin (N=xx)		
Study Week ²	n	Cumulative n	Cumulative %	n	Cumulative n	Cumulative %	p-value ¹
Week 1	XX	XX	xx.x%	XX	XX	XX.X%	0.xxx
Week 2	XX	XX	xx.x%	XX	XX	xx.x%	0.xxx
Week 3	XX	XX	XX.X%	XX	XX	XX.X%	0.xxx
Week 4	XX	XX	XX.X%	XX	XX	XX.X%	0.xxx
Week 5	XX	XX	xx.x%	XX	XX	XX.X%	0.xxx
Week 6	XX	XX	xx.x%	XX	XX	XX.X%	0.xxx
Week 7	XX	XX	XX.X%	XX	XX	XX.X%	0.xxx
Week 8	XX	XX	XX.X%	XX	XX	XX.X%	0.xxx
Week 9	XX	XX	XX.X%	XX	XX	XX.X%	0.xxx
Week 10	XX	XX	XX.X%	XX	XX	XX.X%	0.xxx
Week 11	XX	XX	xx.x%	XX	XX	XX.X%	0.xxx
Week 12	XX	XX	xx.x%	XX	XX	XX.X%	0.xxx
Week 13	XX	XX	XX.X%	XX	XX	XX.X%	0.xxx

Fisher's exact test

Numbers and percentages are based on subjects that participated through a given week

Table 10: Number and Percent of Subjects with Drinking Data Provided by the Brief Drinking Questionnaire instead of the TLFB

	J	Placebo	Ox	ytocin	
Study Week	n	%	n	%	p-value ¹
Week 3	XX	xx.x%	XX	xx.x%	0.xxx
Week 4	XX	xx.x%	XX	xx.x%	0.xxx
Week 5	XX	xx.x%	XX	xx.x%	0.xxx
Week 6	XX	xx.x%	XX	xx.x%	0.xxx
Week 7	XX	xx.x%	XX	xx.x%	0.xxx
Week 8	XX	xx.x%	XX	xx.x%	0.xxx
Week 9	XX	xx.x%	XX	xx.x%	0.xxx
Week 10	XX	xx.x%	XX	xx.x%	0.xxx
Week 11	XX	xx.x%	XX	xx.x%	0.xxx
Week 12	XX	xx.x%	XX	xx.x%	0.xxx
Overall	XX	xx.x%	XX	xx.x%	0.xxx

¹Fisher's exact test

Note only rows with values above 0 will be presented

Table 11: Demographic Characteristics

	Placebo	Oxytocin	Total	
Characteristic	(N=xx)	(N=xx)	(N=xxx)	p-value ¹
Age (years)		`	, ,	0.xxx
N	XX	XX	XX	
Mean (SD)	xx.x (xx.xx)	xx.x (xx.xx)	xx.x (xx.xx)	
Median	xx	XX	XX	

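### SAP 5.1.6 counts a subject lost part-way with no recorded heavy (or drinking) day as a responder for the whole window, and no planned sensitivity analysis or summary table shows the effect

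*SAP*

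**What the plan says.** SAP 5.1.6 defines both rates over "the number of subjects with at least one day of non-missing drinking data during the period of interest". The numerator is everyone in that group with no heavy (or no drinking) day in the window. Nothing requires the window to be observed to its end. By contrast, SAP 5.1.5 and 5.1.7 need at least 3 observed days for a weekly value, and SAP 5.1.8 needs a week of data per month for the WHO endpoints.

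On missing data, SAP 9.5.1 states "No imputation will be done for analysis of secondary endpoints". Protocol 11.4.3 agrees ("These analyses will be performed using the Full Analysis Set subjects with no imputation for missing data"), as does the Protocol Synopsis ("No imputation will be used for the analysis of secondary endpoints"). The one missing-data sensitivity analysis is for the primary endpoint: "a sensitivity analysis will be performed on the primary endpoint using multiple imputation for missing drinking data".

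Three provisions recover later drinking data:
- TLFB catch-up after a missed visit (Protocol 10.32).
- Telephone TLFB for a withdrawing subject who agrees (Protocol 10.32, SAP 5.1.1).
- The Brief Drinking Questionnaire (BDQ), for a subject who "is willing to be contacted by phone at the week most proximal to dropout" (Protocol 10.12). SAP 9.5.1 uses its answers for these two endpoints.

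On reporting, SAP 9.7 says "The research participation rate, defined as percentage of subjects with complete drinking data, will be compared between treatment groups". Table 9 carries the note "Numbers and percentages are based on subjects that participated through a given week", and Table 10 counts BDQ use. Tables 49-64 give responders yes/no and the models.

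**The concern.** These are the first two secondary endpoints in SAP 3.3.2. Taken together, the rules score a subject last seen at Week 4, with seven clean days, as having no heavy drinking days over 70 days. A recorded heavy (or drinking) day makes a subject a non-responder, and a subject with no data in the window leaves the denominator. Errors from partial follow-up therefore run one way: they turn unobserved non-responders into responders. If one arm loses more subjects, the comparison tilts toward that arm.

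The three recovery routes help only for subjects who stay in contact or agree. A BDQ taken near dropout need not reach the end of the window. Participation is compared between arms, but no planned table says how many counted responders have incomplete windows.

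**Working it through.** **Inputs from the documents.** SAP 7.0 gives 50 per arm and 12% attrition: 100 x 0.88 = 88, or 44 analysed and 6 lost per arm. Its power statement reproduces: 44 per arm, d = 0.60 and two-sided 0.05 give 0.804 (normal) or 0.795 (noncentral t) against 0.80. That concerns the primary endpoint; no rate or power is given for the responder endpoints. Visits fall at Weeks 2, 3, 4, 6, 8, 10 and 13 (SAP 3.2), and each TLFB runs to the day before the visit (SAP 5.1.1). A last on-schedule visit at Week w therefore gives 7 x (w - 3) maintenance days: 0, 7, 21, 35 or 49 of 70 for Weeks 3, 4, 6, 8 and 10.

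**Assumptions, not in the documents.** Each subject has a daily heavy-drinking probability drawn from Beta(a,b) and constant in time. There is no drug effect. All 12% are lost with no further data, independently of drinking, with the last visit equally likely at the five weeks above (2.4% each).

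**Formula.** P(no heavy day in D days) = B(a, b+D)/B(a, b). For Beta(1,2) this is 2/(D+2).

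**Beta(1,2), Weeks 3-12.**
- True rate: 2/72 = 2.78%.
- SAP 5.1.6: [0.88 x 2/72 + 0.024 x (2/9 + 2/23 + 2/37 + 2/51)]/0.976 = (0.02444 + 0.00966)/0.976 = 3.49%. Week 3 losses have no days and leave the denominator.
- Missing = non-responder: 0.88 x 2/72 = 2.44%.
- False responders per 100 randomised: 2.4 x (0.4025 - 4 x 2/72) = 0.70.
- Share of counted responders with incomplete windows: 0.00966/0.03410 = 28%.

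| Daily risk | True % | SAP 5.1.6 % | Missing = non-responder % | False responders per 100 |
|---|---|---|---|---|
| Beta(2,2) | 0.1 | 0.3 | 0.1 | 0.2 |
| Beta(1,1) | 1.4 | 1.8 | 1.2 | 0.4 |
| Beta(1,2) | 2.8 | 3.5 | 2.4 | 0.7 |
| Beta(0.5,1) | 10.5 | 11.4 | 9.3 | 0.9 |
| Beta(0.3,0.7) | 21.5 | 22.4 | 18.9 | 0.9 |

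The incomplete-window share is 17% for Beta(0.5,1) and 13% for Beta(0.3,0.7).

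**Variations under Beta(1,2)** (true / SAP 5.1.6 / missing = non-responder):
- Weeks 5-12: 3.4/4.1/3.0%. Weeks 9-12: 6.7/7.1/5.9%. Month 2: 6.7/7.1/6.0%.
- Only 3% or 6% lost to all contact, Weeks 3-12: 2.9% or 3.1% reported, 0.2 or 0.3 false responders per 100.
- Heavier-drinking half twice as likely to be lost (simulated), Weeks 3-12: 2.8/3.3/2.6%.
- All loss after the Week 10 visit, Weeks 9-12: 0.88 x 2/30 + 0.12 x 2/9 = 8.53% reported against 6.7% true; 12 x (2/9 - 2/30) = 1.87 false responders per 100.
- Few observed days: Protocol 7.7 allows a 3-day visit window, so a Week 3 visit 1 to 3 days late leaves 1 to 3 maintenance days. The chance that these are clean is 2/3, 2/4 or 2/5 (67%, 50%, 40%), against 2/9 (22%) at 7 days. The table above excludes such cases.

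**Unequal loss, 6% v 18%, Weeks 3-12.** Null gap in favour of the arm with more loss, SAP 5.1.6 then missing = non-responder: Beta(1,2) +0.7 v -0.3 points; Beta(0.5,1) +0.9 v -1.3; Beta(0.3,0.7) +0.9 v -2.6.

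**Null rejection.** 20,000 simulated trials per scenario, Fisher's test, Beta(1,2), Beta(0.5,1) and Beta(0.3,0.7), with 12/12, 6/18 and 5/25% loss: 0.6% to 3.9% under SAP 5.1.6 and 0.1% to 5.2% under missing = non-responder. SAP 9.4.2 uses Fisher only below 5 events. With a treatment-only Wald logistic model otherwise, rejection under SAP 5.1.6 was about 0.0% to 5.0%.

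**The case against.** The endpoints are secondary and unadjusted for multiplicity, in what Protocol 11.4.11 calls a pilot study. Protocol 7.14 keeps subjects in the study after they stop drug, and 7.10 and 7.15 seek final assessments at early withdrawal, so loss to all contact may be well under 12%. Listing 16 (daily drinks), Listing 17 (any drinking or heavy drinking since the last visit) and Listing 1 (discontinuation date) allow a hand count, and SAP 9.2 presents missing observations between groups. Missing = non-responder is often more biased than the current rule.

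All of this stands, and it limits the point to a missing robustness check. It does not remove it: a hand count from listings is not a by-arm summary, and none of these provisions changes how a subject lost with clean data is scored.

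A reader might infer something stronger. If every lost subject were clean, each arm's rate would rise by 6/50 = 12 points. Holding the retained rate at 10% and splitting the 12 losses 9 v 3 or 12 v 0 would then give null rejection of 19% or 84%. The documents do not support this. They give no such share or imbalance, and on-schedule visits leave either no maintenance days or at least seven. Across the five scenarios, only about 2% to 31% of lost subjects with data would be clean. The opposite inference, that the documents show the effect to be small, is not supported either: they give no responder rates.

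**Conclusion.** The point holds as a minor one. The rule classifies some unobserved time as success, the bias is upward and toward the arm with more loss, and no planned summary or sensitivity analysis shows its extent. Under the stated assumptions it is 0.2 to 0.9 false responders per 100 over Weeks 3-12, rising to 1.9 per 100 in the extreme-timing case for Weeks 9-12. Null rejection above 5% is not shown under the current rule. These figures depend on a daily risk that is constant in time and on on-schedule last visits. The bias could be larger if loss follows relapse, is more unbalanced than assumed, or leaves only a few observed days. The primary endpoint and its power are unaffected.

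**What to change.** Keep SAP 5.1.6 as the main analysis. For both endpoints and every window in SAP 9.4.2.1, pre-specify a sensitivity analysis on the Full Analysis Set. A subject is a responder only if TLFB or BDQ data cover the window to its end with no heavy (or drinking) day, and otherwise a non-responder. Report by arm the number of responders under SAP 5.1.6 whose windows are incomplete, with their observed days.

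State the exception beside the no-imputation sentence in SAP 9.5.1. Align Protocol 11.4.3 and the Synopsis if the sponsor considers it necessary; Protocol 11.1 already lets the SAP add exploratory analyses.

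The cost is one SAP paragraph and a modest set of extra tables, or added rows in Tables 49-64. The downside is that missing = non-responder is biased downward and counts against the arm with more loss. It should be read as a lower bracket beside the current rule, not as its replacement. A one-week minimum like that in SAP 5.1.8 would remove only subjects with 1 to 6 observed days, from late or off-schedule last visits, and would not solve the problem alone.
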